#### Table 10 Construction of rhinitis/rhinoconjunctivitis CSMS in MT-11

	Rhinitis score	Rhinoconjunctivitis score
Symptom Scores		
Rhinitis symptoms		
Runny nose	0-3	0-3
Blocked nose	0-3	0-3
Sneezing	0-3	0-3
Itchy nose	0-3	0-3
Conjunctivitis symptoms		
Red/itchy eyes		0-3
Watery eyes		0-3
Daily symptom score (DSS) 	0-3	0-3
Medication score		
Step 1: Azelastine eye drops		1
Step 1: Desloratadine tablets or	1	1
Desloratadine oral solution		
Step 2: Mometasone furoate nasal spray	2	2
Daily medication score (DMS) 	0-2	0-2
Combined symptom and medication score (CSMS), DSS (0-3) + DMS (0-2)	0-5	0-5

 The DSS is calculated as the sum of the individual symptom scores divided by the number of symptoms and ranges from 0-3.

 The DMS is the score of highest medication step used. No medication use means a score of 0. The DMS range from 0-2.

#### 7.1.2.4 Average daily asthma VAS and average daily rhinoconjunctivitis VAS

The average daily asthma VAS and the average daily rhinoconjunctivitis VAS is for each subject and each visit (V2, V5, V6, V7, V8, V9, V10, V11) calculated as the average of non-missing records during the 14 days of eDiary assessment.

#### 7.1.2.5 The proportion of days with nocturnal awakening

Nocturnal awakenings due to asthma requiring SABA is recorded daily during the periods of eDiary recording.

The proportion of days with nocturnal awakenings due to asthma requiring SABA rescue medication is for each subject and each visit (V2 (baseline), V5 (at 4 months), V6 (at 8 months), V7

Type of document Document ID	Date: Version:	11-Aug-2022 4.0	
	Status:	Final	
INTERNAL USE	Page:	54 of 79	

(at 12 months), V8 (at 16 months), V9 (at 20 months), V10 (at 24 months) and V11 (25-29 months)) calculated as the number of events divided by the number of Diary records.

#### 7.1.2.6 The proportion of days with SABA use

SABA use is recorded daily during the periods of eDiary recording.

The proportion of days with SABA use is for each subject and each visit (V2 (baseline), V5 (at 4 months), V6 (at 8 months), V7 (at 12 months), V8 (at 16 months), V9 (at 20 months), V10 (at 24 months) and V11 (25-29 months)) calculated as the number of events divided by the number of Diary records.

#### 7.1.2.7 The average asthma DSS

Asthma symptoms are recorded daily during the periods with eDiary recording.

The asthma symptoms consist of 4 asthma symptoms (cough, wheezing, chest tightness and shortness of breath) which are scored from 0 to 3 as follows:

- 0 = no symptoms
- 1 = mild symptoms
- 2 = moderate symptoms
- 3 = severe symptoms

The asthma DSS is the sum of all 4 individual asthma symptom scores and ranges from 0 to 12.

The average asthma DSS is for each subject and each visit (V2, V5, V6, V7, V8, V9, V10, V11) calculated as the average of non-missing records during the 14 days of eDiary assessment.

#### 7.1.2.8 Daily SABA usage

SABA usage is recorded daily during the periods with eDiary recording.

The salbutamol inhaler should be used when necessary, according to the dosage instruction for salbutamol inhaler: Up to 2 doses 4 times per day.

The recommended daily dose for children (5-11 years) is 200  $\mu$ g. The recommended daily dose for adolescent (12-17 years) is 800  $\mu$ g.

The number of daily recommended SABA doses used is calculated each day as the dose used divided by the recommended daily dose.

The average daily number of (recommended) doses of SABA is for each subject and each visit (V2, V5, V6, V7, V8, V9, V10, V11) is calculated as the average of non-missing records during the 14 days of eDiary assessment.

Type of document	Date:	11-Aug-2022	 	_
Document ID	Version:	4.0	1 8	
	Status:	Final		
INTERNAL USE	Page:	55 of 79		

#### 7.1.3 Pharmacodynamics endpoints

Changes from baseline in log10 transformed specific IgE, IgE-BF and log10 transformed IgG4 against *D. pteronyssinus* and *D. farinae* measured at V7 and V11.

#### 7.1.4 Imputation of dates

When establishing how many historical asthma exacerbations a subject has within a given period, a partial end date is imputed to be as late as possible but no later than the date of informed consent.

When calculating the duration of medical history of asthma or rhinitis, a partial start date is imputed to be as early as possible.

For the purpose of defining which adverse events are treatment emergent or calculating a duration, any partial start date is imputed of the adverse event is imputed to be as early as possible, if the start date could possibly be the date of first dose of IMP given the partial date and the end date if any, it is instead imputed to be the date of first dose.

Any partial date of last dose is imputed to as late as possible but no later than the date of last contact. Missing dates of last dose are imputed as the date of last contact.

To be able to calculate the age at the start of a given diary period, the partial date of birth of each subject is imputed to be as late as possible taking the age at screening, the date of screening, the age recorded for pulmonary function tests at baseline, and the corresponding date into consideration.

Type of document Document ID	Date: Version:	11-Aug-2022 4.0	1.1	
	Status:	Final		
INTERNAL USE	Page:	56 of 79		

# 7.2 Appendix 2: Further details pertaining to statistical analyses

#### 7.2.1 Primary endpoint analysis

If the NB regression model fails to converge, a Poisson regression model with an overdispersion parameter will be applied instead for the primary efficacy analysis with the same covariates and offset as for the NB regression. If this model also fails to converge, the Poisson regression model without overdispersion will be used for the primary efficacy analysis.

The treatment group comparison will be performed using a Log Likelihood Ratio (LR) test derived from the NB regression analysis. The null hypothesis is that the rate of clinically relevant asthma exacerbations is equal for the active group and the placebo group. The alternative hypothesis is that the rate of clinically relevant asthma exacerbations is different for the active group and the placebo group. The primary outcome is the resulting p-value from the LR test reported together with the ratio of the rates and Wald 95% confidence intervals. The result of the primary efficacy analysis is considered successful when the p-value is below 0.05.

### 7.2.2 Multiple imputation

Imputation will be done using the method of unrestricted random sampling with replacement (seed=686), and 500 multiple imputed datasets will be created. For subjects discontinuing treatment in period 4 (both treatment and placebo arms), the number of clinically relevant asthma exacerbations for the remaining time of period 4 (from the treatment discontinuation to end of period 4) will be calculated based on the imputed rate (imputed events by imputed exposure time) from the completers in the placebo group. For a subject who discontinues treatment, the number of events up until discontinuation is calculated. For the rest of the observation period, the number of events is calculated from the imputed rate as follows:

Imputed events =  $\frac{imputed \ number \ of \ exents}{imputed \ exposure \ time} \cdot (time_{planned \ exposure} - time_{exposure})$ 

where:

 $time_{planned\ exposure} = planned\ end\ date - actual\ start\ date$   $planned\ end\ date = 30th\ of\ April\ 2020, 2021, 2022\ depending\ on\ cohort$  $time_{exposure} = the\ individual\ exposure\ time\ for\ the\ subject$ 

Then the total number of events is calculated as the sum of the events prior to discontinuation of treatment and the number of imputed events. The total exposure time is planned exposure time.

In the sensitivity analysis (sensitivity analysis 2 in Error! Reference source not found.), each of the 500 multiple imputed datasets will then be analysed using the negative binomial regression model specified for the primary efficacy analysis. The resulting estimates and standard errors for the multiple data sets are finally pooled to 1 single estimate and associated standard error using the method of Rubin **(Rubin D. B 1987)**. If a substantial number of the 500 analyses fails to converge (>1%), a Poisson regression model with an overdispersion parameter will additionally be applied in the analysis of the 500 imputed datasets using the strategy described in section **7.2.1**. If 1% or less of the 500 analyses fails to converge, additional imputed datasets will be created and analysed until in total 500 analyses converge.

Type of document	Date:	11-Aug-2022	
Document ID	Version:	4.0	
	Status:	Final	
INTERNAL USE	Page:	57 of 79	

#### 7.2.3 Secondary endpoints analysis

In the analysis of the first and second key secondary endpoints, the marginal model will be estimated using a GEE- approach. The treatment effect on the logit scale is an average treatment effect across all visits and will be estimated as a contrast of parameters in the marginal model. The corresponding odds ratio for proportions of days with nocturnal awakening requiring SABA of active treatment relative to placebo will be presented together with the coherent p-value and 95% confidence limit. If convergence issues are encountered for the marginal logistic regression model, other working covariance structures will be considered (e.g. an independence structure (IND)).

In the analysis of the third key secondary endpoint and the additional secondary endpoints, the treatment effect is the average of the treatment effect across all visits and will be estimated as a contrast of the parameter estimates in the MMRM model. The corresponding p-value will be calculated by means of a t-test with Kenward-Roger degrees of freedom approximation. LSMeans by treatment group will be displayed. In addition, the relative difference will be reported together with 95% confidence limits calculated based on Fieller's theorem for non-transformed data. In models where data is square-root transformed, the absolute difference will be calculated based on a second-order Taylor series expansion.

If an MMRM model with an unstructured covariance matrix fails to converge, unstructured correlations (UNR), Toeplitz (Toep) or compound symmetry (CS) will be used instead, prioritized in the listed order. If the MMRM model still fails to converge, a reduced model is used to estimate starting values for the type of covariance structure mentioned above. If the use of starting values will still not lead to convergence, the model is reduced by eliminating effects backwards (i.e. first region then age group).

If a Cox proportional hazards regression models fails to converge in the analysis of time to events, e.g. due to few events, then Firth's penalized maximum likelihood estimation is used.

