- I6. ≥3 clinically relevant asthma exacerbations⁴⁶ in the past two years or ≥2 clinically relevant asthma exacerbations in the past year or ≥1 severe asthma exacerbation⁴⁷ in the past year prior to randomisation while being on asthma controller medication (low dose ICS plus LABA or medium/high dose ICS with or without LABA)⁴⁸. The asthma controller medication at the screening visit must be at a dose equivalent to or below the dose the subject received before the last asthma exacerbation occurred
- 17. One or more of the following within the past 4 weeks prior to randomisation:
 - a. Daytime asthma symptoms more than twice/week
 - b. Any nocturnal awakening due to asthma which require use of SABA rescue medication
 - c. SABA rescue medication needed for treatment of asthma symptoms more than twice/week
 - d. Any activity limitation due to asthma
- I8. Lung function measured by FEV₁ ≥ 70% of predicted value⁴⁹ or according to local requirements while on background treatment following at least a 6-hour washout of SABA at screening and randomisation
- 19. Clinical history of HDM AR within the last year prior to randomisation⁵⁰
- I10. An average TCRS>0 during the baseline period (period 2)
- I11. Positive specific IgE (defined as ≥class 2, ≥0.70 kU/I) against *D. pteronyssinus* and/or *D. farinae* at screening
- 112. Positive SPT⁵¹ to *D. pteronyssinus* and/or *D. farinae* at screening
- 113. Subject willing and able to comply with trial protocol

⁴⁹ Interpretation of normal range for spirometric test should be based on the Quanjer reference equations (Quanjer et al. 1995).

⁴⁶ A clinically relevant asthma exacerbation is defined as at least one of the following criteria: a) Doubling of ICS dose compared to background treatment, b) Systemic corticosteroids for treatment of asthma symptoms for at least 3 days, c) Emergency room visit due to asthma, requiring systemic corticosteroids or d) Hospitalisation for more than 12 hours due to asthma, requiring treatment with systemic corticosteroids.

⁴⁷ A severe asthma exacerbation is defined as at least one of the following: a) Systemic corticosteroids for treatment of asthma symptoms for at least 3 days, b) Emergency room visit due to asthma, requiring systemic corticosteroids or c) Hospitalisation for more than 12 hours due to asthma, requiring treatment with systemic corticosteroids.

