Percentage predicted FEV₁ assessed every 4 month after randomisation will be analysed by means of a MMRM. The model includes treatment, visit and age group (<12 years/≥ 12 years) and country as fixed factors, the baseline percentage predicted FEV₁ as a covariate and subject as a random effect. Different residual errors for each treatment group will be speficied and the within-subject correlated errors is modelled as TOEP. A between treatment comparison will be performed by means of a t-test with Kenward-Roger degrees of freedom approximation. The resulting p-value will be reported together with the difference in adjusted means. In addition the relative difference will be reported together with 95% confidence limits calculated based on Fieller's theorem.

The average TCRS over the two week diary assessment (before V5, V6, V7, V8, V9, V10 and V11) will be analysed by means a MMRM. The analysis includes the square root transformed average TCRS as response variable; treatment, visit, and treatment-by-visit interaction, age group (<12 years/≥ 12 years) and country as fixed factors; the square root transformed baseline score as a covariate and subject as random effects. Different residual errors for each treatment group is specified. For each visit, the between treatment comparison will be performed by means of a t-test. The resulting p-value will be reported together with the difference in back-transformed adjusted means. As additional information the relative difference of the back-transformed adjusted means is reported together with 95% confidence limits. The latter is calculated based on Fieller's theorem.

The average rhinitis DSS, the average rhinitis DMS, the average total combined rhinoconjunctivitis score, the average rhinoconjunctivitis DSS, the average rhinoconjunctivitis DMS will be analysed using a similar MMRM model as described for the average TCRS.

The average asthma DSS score and ACQ/ACQ-IA will also be analysed by means of a MMRM model.

Time to first severe asthma exacerbation and time to first clinically relevant asthma exacerbation will be analysed by means of a Cox proportional hazards regression analysis. The model is stratified for country and includes treatment group as a factor.

The severe asthma exacerbations will be analysed by means of a NB regression model with treatment group, agegroup (<12 years/ \geq 12 years) and country as factors and the logarithm of the duration time in years in period 4 as an offset value.

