Percentage predicted FEV1 assessed every 4 months after randomisation (at V5, V6, V7, V8, V9, V10 and V11) will also be analysed by means of an MMRM model. The response variable is the percentage predicted FEV1. Treatment, visit, treatment-by-visit interaction, age group (<12 years/ $\geq$  12 years) and region will be included as fixed effects. Baseline percentage predicted FEV1 (measured at visit 3) will be included as a covariate. Different residual errors for each treatment group will be specified and the within-subject correlated errors are modelled by an unstructured covariance. The treatment effect is the average treatment effect across all visits. The between treatment comparison will be performed by means of a t-test with Kenward-Roger degrees of freedom approximation (Kenward and Roger 1997). For both the overall treatment effect and the effect per visit, the resulting p-value will be reported together with the difference in adjusted means.

In addition, the absolute treatment estimates by visit and 95% confidence intervals will be plotted from the MMRM model.

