### 4.3.2.3 Predicted FEV1

Change from baseline in percentage predicted FEV1 will be analysed by means of an MMRM model as for the endpoint "Percentage predicted FEV1".

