#### Endpoints

- A new additional secondary endpoint has been added: "Change from baseline in percentage predicted FEV1".
- The key secondary endpoint for SABA use has been changed from a continuous endpoint (average daily doses) to a binary endpoint (proportion of days). The reason is that many subjects do not use any SABA and the resulting excessive number of zeros are challenging to model as a continuous variable. The continuous endpoint "Average daily dose of SABA" will instead be analysed as an additional secondary endpoint.
- Explorative endpoints have been renamed to Other endpoints.

- If any subject exceeds the recommended daily dose of a symptomatic medication for rhinitis or rhinoconjunctivitis, the maximal daily score will be used and not the actual score as specified in the protocol.
- Additional description of how safety endpoints are summarised are added:
  - Duration in minutes of the solicited AEs occurring on first day of IMP intake, treatment-emergent anaphylactic reactions, anaphylaxis and/or systemic allergic reactions, TEAEs treated with adrenaline/epinephrine, treatment-emergent severe local swelling or oedema of the mouth and/or throat, treatment-emergent eosinophilic oesophagitis, medication error, local application site TEAEs, onset and resolution time in days for most frequent TEAEs (≥2% of subjects in active group), onset and resolution time in days for local application site TEAEs, drug abuse, misuse and overdose.

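### SAP 7.2.3 attaches a relative difference with Fieller limits to two change-from-baseline endpoints, where the likely divisor is a mean change that may be near zero

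*SAP*

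**What the plan says.** SAP 7.2.3 sets its scope with the words "In the analysis of the third key secondary endpoint and the additional secondary endpoints". Within that scope it describes the MMRM treatment effect, its p-value and the least squares means by arm, and then adds that "the relative difference will be reported together with 95% confidence limits calculated based on Fieller's theorem for non-transformed data". No endpoint is excepted.

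Two change scores fall inside that sentence.

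- **Change from baseline in percentage predicted FEV1.** SAP 4.8 (Endpoints) records it: "A new additional secondary endpoint has been added". SAP 4.3.2.3 states that it "will be analysed by means of an MMRM model as for the endpoint" percentage predicted FEV1, with no transformation.
- **Change from baseline in IgE-BF.** SAP 4.3.2.7 analyses it by a similar MMRM and without the log transformation used for IgE and IgG4. The IgE and IgG4 changes are transformed, so they lie outside the sentence.

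The main text for the FEV1 model (SAP 4.3.1.3) asks for less: "the resulting p-value will be reported together with the difference in adjusted means". In the protocol (15.8), the only FEV1 endpoint with a ratio was the level, percentage predicted FEV1: "In addition the relative difference will be reported together with 95% confidence limits calculated based on Fieller's theorem".

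**The concern.** A relative difference is useful when the reference mean is well away from zero. Percentage predicted FEV1 meets that condition, because entry requires "Lung function measured by FEV₁ ≥ 70% of predicted value" (or the local requirement). A mean change from baseline need not meet it. If the divisor is the placebo mean change, a small absolute effect can appear as a very large percentage of either sign, and the confidence set may be the whole line or two separate pieces.

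The SAP has no rule for a divisor near zero or for an unbounded set. The report could then carry a percentage effect on lung function that misleads in size or direction, or the team would have to decide after unblinding what to print.

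**Working it through.** **Is the output required?** SAP section 1 describes Appendix 2 as the detailed account of how to code the analyses, and SAP section 4 says that its text and the appendices together specify them. Section 7.2.3 introduces the ratio as an addition. The silence of 4.3.1.3 and 4.3.2.7 therefore does not remove it.

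**When is the Fieller set bounded?** Let p and a be the adjusted mean changes on placebo and active, treated as independent with common standard error s, and let r = a/p. The 95% set holds all r with (a - rp)² ≤ 1.96²·s²·(1 + r²). It is a bounded interval only if p² > 1.96²·s², that is, only if the placebo mean change itself differs from zero at the two-sided 5% level. The relative difference is r - 1.

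**Inputs.** The documents state no figure to reproduce, and no placebo change or SD. The SAP gives 533 randomised (1.2) and 9 subjects at site 613 removed from the FAS (3.1). That leaves 533 - 9 = 524, or about 262 per arm at 1:1. Assumed here: SD of the visit-averaged FEV1 change 8 to 12 percentage points, and 200 to 240 subjects per arm. Then s lies between 8/√240 = 0.52 and 12/√200 = 0.85. The set is unbounded when the estimated placebo change is within 1.96·s of zero, about ±1.0 to ±1.7 points.

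**Probability of an unbounded set.** For a true placebo change m, P = Φ(1.96 - m/s) - Φ(-1.96 - m/s).

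| True placebo change (points) | s = 0.52 | s = 0.85 |
|---|---|---|
| 0 | 95% | 95% |
| 0.5 | 84% | 91% |
| 1 | 51% | 78% |
| 2 | 3% | 35% |
| 3 | 0% | 6% |
| 5 | about 0% | about 0% |

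Wider assumptions (SD of a single-visit change 8 to 15, correlation between the seven visits 0.3 to 0.7, 200 to 262 per arm) use s = SD·√((1 + 6ρ)/(7n)), which runs from 0.31 to 0.91. The probabilities are then 64-92% at 0.5, 11-81% at 1, 0-41% at 2 and 0-9% at 3 points.

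**Size and sign of the ratio.** Hold the treatment difference at +1 point. Then (a - p)/p is -200% at a placebo change of -0.5, +1000% at +0.1, +200% at +0.5 and +50% at +2. On the level scale (assumed 90 against 91) it is 1/90 = +1.1%.

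**Fieller sets for observed means, at s = 0.70, inside the assumed range:**

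- placebo -0.5, active 0.5: the whole line;
- placebo 1, active 2: everything except the stretch from -601% to -52%;
- placebo 2, active 3: -33% to +399%;
- placebo 3, active 4: -24% to +161%;
- level 90 against 91: -1.0% to +3.3%.

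No comparable calculation was made for IgE-BF, because the documents give nothing on its scale or variability.

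**What the rest of the change analysis adds.** Write the FEV1 model as Y = τ·treatment + other terms + β·B, where B is the visit 3 baseline with one common slope. Subtracting B from both sides gives Y - B = τ·treatment + other terms + (β - 1)·B. Only the slope moves. The treatment difference, its standard error and its p-value equal those of the key secondary FEV1 analysis.

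**The case against.** The strongest reply is that the endpoint-specific sections never ask for this ratio. SAP 4.3.1.3 and 4.3.2.7 list p-values and differences in adjusted means, whereas SAP 4.3.2.4 names the relative difference and Fieller limits where they are wanted. Section 7.2.3 also cannot apply literally to every additional secondary endpoint, since some are analysed by Cox, negative binomial or logistic models. On this view the fault is loose appendix wording, not a choice to analyse change scores as ratios. That is fair as to intent. It does not remove the instruction, because the appendix is part of the specification.

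The second reply is that the instability depends on a placebo change that nobody has stated. This stands. A reader might infer that the interval will usually fail, and the documents do not support that: at 3 points or more the set is nearly always bounded under the assumptions above. Nor does the Fieller set ever fail to exist; what can fail is a finite interval.

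Third, the SAP does not say that placebo is the divisor. It is the natural reading, by analogy with the rate reduction relative to placebo in SAP section 5. If the active mean were the divisor, it would also be a mean change that could lie near zero, so the gap in the text does not cure the problem.

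**Conclusion.** The point holds as a minor defect of specification. As written, SAP 7.2.3 requires a ratio and Fieller limits for two change scores, does not define the divisor, and has no rule for a divisor near zero. For FEV1 the chance of an unbounded set runs from 95% at a true placebo change of 0 to about 0% at 5 points. It is 51-78% at 1 point and 3-35% at 2 points. These figures rest on an assumed standard error of 0.52 to 0.85 and on placebo being the divisor.

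Three stronger readings should be resisted.

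- Not every untransformed endpoint is affected: ACQ/ACQ-IA is a 0 to 6 level, not a change.
- No conclusion of the trial is at risk. The p-value and the absolute difference are unaffected, the change endpoints are outside the test hierarchy in SAP 2.1, and no decision rule uses the ratio.
- The exact repetition of the key secondary FEV1 result might suggest that the SAP offers the change score as separate evidence. It does not: it lists the change as an additional secondary endpoint with no estimand (SAP 1.1.9). Showing a level beside its change is a choice of presentation.

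**What to change.** In SAP 7.2.3:

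- limit the relative difference and Fieller limits to endpoints analysed as levels, such as percentage predicted FEV1 and ACQ/ACQ-IA;
- state that the divisor is the placebo adjusted mean;
- for change-from-baseline endpoints (percentage predicted FEV1 and IgE-BF), report only the absolute difference in adjusted means with its 95% CI.

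Optionally, note in SAP 4.3.2.3 that, with baseline as a covariate, the treatment difference and p-value for the FEV1 change equal those of the key secondary FEV1 analysis.

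The cost is a few sentences of SAP text and one less output column. No data, model or test changes.
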